6.1.6 Pregnancy

Pregnancy in a study subject must be reported to AbbVie within 1 working day of the site becoming aware of the pregnancy. Administration of study drug may be continued at the investigator's discretion after discussion with the subject, if the benefit of continuing therapy is felt to outweigh the risk (Section 5.4.1). If a subject is discontinued, the subject will be monitored for SVR in the Post-Treatment Period as described in Section 5.1.3.

Information regarding a pregnancy occurrence in a study subject and the outcome of the pregnancy will be collected for pregnancies occurring up to 30 days after the end of treatment.

Pregnancy in a study subject is not considered an adverse event. The medical outcome for either mother or infant, meeting any serious criteria including an elective or spontaneous abortion, is considered a serious adverse event and must be reported to AbbVie within 24 hours of the site becoming aware of the event.

6.1.7 Toxicity Management

For the purpose of medical management, all adverse events and laboratory abnormalities that occur during the study must be evaluated by the investigator. All adverse events and laboratory abnormalities will be managed and followed to a satisfactory clinical resolution. A toxicity is deemed "clinically significant" based on the medical judgment of

the investigator. The table of clinical toxicity grades "National Cancer Institute Common Terminology Criteria for Adverse Events, Version 4.03" is to be used in the grading of adverse events and laboratory abnormalities, which is available on the Cancer Therapy Evaluation Program (CTEP) website at:

http://evs.nci.nih.gov/ftp1/CTCAE/CTCAE_4.03_2010-06-14_QuickReference_5x7.pdf.

Specific toxicity management guidelines apply to the instances of increases in ALT (Section [6.1.7.1](#)).

6.1.7.1 Management of Transaminase Elevations

If a subject experiences a post-baseline increase in ALT to $> 5 \times \text{ULN}$ which is also $> 2 \times \text{baseline value}$, the subject should have a confirmatory ALT measurement performed.

If, the ALT increase is confirmed to be $> 5 \times \text{ULN}$ which is also $> 2 \times \text{baseline value}$, the recommendations below should be followed:

- Complete hepatic questionnaire.
- Evaluate for alternate etiology of ALT elevation; document in the source, update the medical history and concomitant medications eCRF (if applicable), and obtain Anti-HAV IgM, Anti-HAV IgG, Anti-HBc IgM, Anti-HBc Total, Anti-HBs, HBV DNA, HBsAg, Anti-HEV IgM, Anti-HEV IgG and HEV RNA, and other additional tests, as appropriate.
- Manage the subject as medically appropriate.
- Repeat ALT, AST, total and fractionated bilirubin, alkaline phosphatase and INR within 1 week. Repeat liver chemistries as indicated until resolution.
- Discontinue study drug if any of the following is observed at any time:
 - ALT level is $\geq 20 \times \text{ULN}$ in the absence of an alternate etiology.
 - Increasing direct bilirubin or INR or onset of symptoms/signs of hepatitis.
 - At the discretion of the investigator.

Alternate management of ALT increases is permitted with approval of the AbbVie Therapeutic Area Medical Director (TA MD).

6.2 Product Complaint

6.2.1 Definition

A Product Complaint is any Complaint (see Section [6.0](#) for the definition) related to the biologic or drug component of the product.

For a product this may include, but is not limited to, damaged/broken product or packaging, product appearance whose color/markings do not match the labeling, labeling discrepancies/inadequacies in the labeling/instructions (example: printing illegible), missing components/product, or packaging issues.

Any information available to help in the determination of causality to the events outlined directly above should be captured.

6.2.2 Reporting

Product Complaints concerning the investigational product must be reported to the Sponsor within 24 hours of the study site's knowledge of the event via the Product Complaint form. Product Complaints occurring during the study will be followed-up to a satisfactory conclusion. All follow-up information is to be reported to the Sponsor (or an authorized representative) and documented in source as required by the Sponsor. Product Complaints associated with adverse events will be reported in the study summary. All other complaints will be monitored on an ongoing basis.

Product Complaints may require return of the product with the alleged complaint condition. In instances where a return is requested, every effort should be made by the investigator to return the product within 30 days. If returns cannot be accommodated within 30 days, the site will need to provide justification and an estimated date of return.

The description of the complaint is important for AbbVie in order to enable AbbVie to investigate and determine if any corrective actions are required.

8.0 Statistical Methods and Determination of Sample Size

8.1 Statistical and Analytical Plans

Analyses will occur after subjects have completed the PT Week 12 Visit or prematurely discontinued study. The first analysis will occur after all HCV GT1, 2, 4, 5, and 6-infected subjects have completed the PT Week 12 Visit or prematurely discontinued study; the second analysis will occur after all HCV GT3-infected subjects have completed the PT Week 12 Visit or prematurely discontinued study; the third and final analysis will occur after all subjects have completed or prematurely discontinued from the study.

SAS® (SAS Institute, Inc., Cary, NC) for the UNIX operating system will be used for all analyses. All confidence intervals will be two-sided with an alpha level of 0.05.

Descriptive statistics will be provided, such as the number of observations (N), mean, and standard deviation (SD) for continuous variables and counts and percentages for discrete variables.

Safety analyses will be performed on all subjects who receive at least one dose of study drug.

Efficacy analyses will be performed on the intention-to-treat (ITT) population defined as all enrolled subjects who receive at least one dose of study drug, unless otherwise specified. The Per-Protocol (PP) population includes all enrolled subjects who receive at least one dose of study drug, with the exception of subjects who experience breakthrough, or prematurely discontinue treatment prior to Week 8, or have no HCV RNA value in the SVR₁₂ visit window or later.

The primary and key secondary efficacy analyses will be performed on the PP and ITT populations, as specified. The other secondary efficacy analyses will be performed on the ITT population, unless otherwise specified.

Sensitivity analyses of SVR₁₂, when applicable, will be performed on the intention-to-treat population modified to exclude subjects who were enrolled with ineligible genotypes (e.g., GT3 according to phylogenetic analyses for the group of non-GT3-infected subjects) (mITT-GT), and on the mITT-GT population modified to exclude subjects who did not achieve SVR₁₂ for reasons other than virologic failure (mITT-GT-VF).

No data will be imputed for any efficacy or safety analysis except for analyses of SVR endpoints (HCV RNA data) and PRO questionnaires. HCV RNA values will be selected for the analyses of all SVR endpoints (e.g., SVR₄, SVR₁₂, and SVR₂₄) based on defined visit windows. A backward imputation method will be used to impute missing responses for SVR analyses. Imputation of missing responses on PRO questionnaires is described in Section 8.1.3.

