8.1.4 Resistance Analyses

For all subjects, full length NS3/4A or NS5A from baseline samples will be sequenced by NGS. For subjects who experience virologic failure (OTVF or post-treatment relapse), full length NS3/4A and NS5A genes from the first sample after virologic failure with HCV RNA \geq 1000 IU/mL will be sequenced by NGS. An appropriate subtype specific prototypic reference sequence will be used for comparison with sequences from samples. Subjects treated with study drug who do not achieve SVR₁₂ due to reasons other than virologic failure but have a time point with HCV RNA \geq 1000 IU/mL after treatment discontinuation will have the sample at that time point sequenced.

Only samples with an HCV RNA level of \geq 1000 IU/mL will undergo sequence analysis in order to allow accurate assessment of products of amplification. Therefore, if the HCV RNA level at the time of HCV virologic failure or treatment discontinuation is $<$ 1000 IU/mL, the sample closest in time after HCV virologic failure/treatment discontinuation with an HCV RNA level \geq 1000 IU/mL will be used. Included time

points for analyses on samples from subjects who do not achieve SVR₁₂ are 1) the sample closest in time after failure/discontinuation with an HCV RNA level of \geq 1000 IU/mL, and 2) 24 weeks post-DAA treatment, provided that resistance-associated substitutions were detected by NGS at the time of HCV virologic failure/treatment discontinuation.

For each DAA target, signature amino acid positions and a key subset of amino acid positions are listed in [Table 8](#). Appropriate subtype specific prototypic reference sequence will be used for comparison with sequences from samples.

Table 8. Signature Amino Acid Positions and the Key Subset of Amino Acid Positions

| Target | Signature Amino Acid Positions | Key Subset of Amino Acid Positions |
|-------------------------|---|--------------------------------------|
| GT1 NS3 | 36, 43 (GT1a only), 54, 55, 56, 80, 107, 122, 132 (GT1a only), 155, 156, 158, 168, 170, 175 (GT1b only) | 155, 156, 168 (all GTs) |
| GT2, 3, 4, 5, 6 NS3 | 36, 43, 54, 55, 56, 80, 155, 156, 168 | |
| GT1 NS5A | 24, 28, 29, 30, 31, 32, 54 (GT1b only), 58, 62, 92, 93 | 24, 28, 30, 31, 58, 92, 93 (all GTs) |
| GT2, 3, 4, 5, 6 NS5A | 24, 28, 29, 30, 31, 32, 58, 92, and 93 | |

The following definitions will be used in the resistance analyses:

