#### **5.1.4 Modified Intention-to-Treat (mITT) Populations**

Sensitivity analyses of SVR12 will be performed on the Modified Intention-to-Treat Genotype (mITT-GT) population and Modified Intention-to-Treat Genotype and

Virologic Failure (mITT-GT-VF) population, respectively, as defined below, when applicable.

The mITT-GT population includes subjects who receive at least 1 dose of study drug but excludes the subjects who were enrolled with ineligible genotypes (e.g., GT3 for the group of HCV GT 1, 2, 4, 5 or 6-infected subjects (final HCV genotype as defined in Section 10.8)).

The mITT-GT-VF population includes all subjects in the mITT-GT population defined above by excluding subjects who did not achieve SVR12 for reasons other than virologic failure.

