### **Reasons for SVR12 Non-Response**

Subjects who do not achieve SVR12 (SVR12 non-responders) will be categorized as having:

1. On-treatment virologic failure (see **On-treatment virologic failure** definition, if a subject meets both definitions of **Breakthrough** and **EOT failure**, he or she will be categorized as **Breakthrough** only);
2. HCV reinfection (see definition described earlier);
3. Relapse12 (see **Relapse12** definition);
4. Prematurely discontinued study drug with no on-treatment virologic failure (defined as any SVR12 non-responder who prematurely discontinued study drug [study drug duration < 52 days for subjects assigned to 8 weeks of treatment, and < 77 days for subjects extended to 12 weeks of treatment] and did not meet the **On-treatment virologic failure** definition);
5. Missing follow-up data in the SVR12 window (defined as any subject who completed study drug without data in the SVR12 window after applying the imputation rules and not meeting the definitions of [1], [2], [3], or [4]);
6. Other (defined as any SVR12 non-responder not meeting the definitions of [1] – [5]).

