## 10.6 Efficacy Subgroup Analysis

The subgroup analyses will be performed based on the ITT and mITT-GT-VF populations. The number and percentage of subjects with SVR12 will be presented for the following subgroups:

- HCV genotype and subtype (as defined in Section 10.8);
- Sex (male or female);
- Age (< 65 or ≥ 65 years) and (< 75 or ≥ 75 years);
- Race (White, Black/African-American, Asian, or other) and (black or non-black);
- Ethnicity (Hispanic or Latino, Not Hispanic or Latino);
- Geographic region (North America, Europe, or ROW);
- Baseline BMI (< 30, or ≥ 30 kg/m^2);
- Baseline HCV RNA level (< 800,000 or ≥ 800,000 IU/mL; < 1,000,000 or ≥ 1,000,000 IU/mL);
- Baseline Child-Pugh score (5, 6, or > 6)
- Baseline platelet count (< 100 or ≥ 100 × 10^9/L; < 150 or ≥ 150 × 10^9/L);
- Baseline albumin (< 35 or ≥ 35 g/L);
- Baseline FibroTest (< 0.75 or ≥ 0.75);
- Baseline APRI (≤ 1, > 1 to ≤ 2, or > 2);
- Baseline FIB-4 (< 1.45, ≥ 1.45 to ≤ 3.25, or > 3.25);
- Baseline AST/ALT ratio (≤ 1 or >1);
- Baseline total bilirubin (< 34.2 or ≥ 34.2 umol/L);
- Baseline creatinine clearance (< 60, ≥ 60 to < 90, or ≥ 90 mL/min);
- Baseline eGFR (< 60, ≥ 60 to < 90, or ≥ 90 mL/min/1.73 m^2);
- Subject on stable opiate substitution (yes/no);
- History of diabetes (yes/no);
- Concomitant use of Proton Pump Inhibitors (PPIs) (yes/no).

The 2-sided 95% confidence interval using Wilson's score method will be produced if there are at least 10 subjects in the subgroup.

In addition, stepwise logistic regression will be performed on SVR12 with all subgroup variables used as predictors of response based on the mITT-GT-VF population. Some

variables will be treated as continuous to decrease the chance of separation or quasi-separation and some variables may be eliminated if missing for many subjects.

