## 10.8 Resistance Analyses

For all subjects, full length NS3/4A or NS5A from baseline samples will be sequenced by next generation sequencing (NGS). For subjects who experience virologic failure (on-treatment virologic failure or post-treatment relapse as defined in Section 10.1), full length NS3/4A and NS5A genes from the first sample after virologic failure with HCV RNA  $\geq$  1000 IU/mL will be sequenced by NGS. An appropriate subtype specific prototypic reference sequence will be used for comparison with sequences from samples. Subjects who experience virologic failure (VF) will be referred to as subjects in the primary virologic failure (PVF) population, and a listing by subject that includes HCV genotype/subtype, IL28B genotype, reason for SVR12 non-response, time point(s) sequenced as closest to time of VF, and HCV RNA value at the VF time point(s) will be produced for these subjects. In addition, all listings described below will display HCV genotype/subtype and reason for SVR12 non-response in the subject identifier for each subject. A separate listing will summarize all subjects in the PVF population for whom no sequencing was performed (e.g., lost to follow-up while HCV RNA  $\leq$  1000 IU/mL).

Subjects treated with study drug who do not achieve SVR12 due to reasons other than virologic failure (prematurely discontinued study drug with no on-treatment virologic failure, HCV reinfection, missing SVR12 data, or other reasons as described in Section 10.1, Reasons for SVR12 Non-Response), but have a time point with HCV RNA  $\geq$  1000 IU/mL after treatment discontinuation will have the sample at that time point sequenced. These subjects will be referred to as the non-PVF population. A listing of all subjects in the non-PVF population with post-baseline sequencing available will be created that is similar to the listing of subjects in the PVF population with post-baseline sequencing available.

Included time points for analyses on samples from subjects who do not achieve SVR12 are 1) the sample closest in time after failure/discontinuation with an HCV RNA level of  $\geq$  1000 IU/mL, and 2) 24 weeks post-DAA treatment, provided that resistance-associated substitutions were detected by NGS at the time of HCV virologic failure/treatment discontinuation.

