- The number and percentage of subjects with baseline polymorphisms at signature amino acid positions at detection thresholds of 2% and 15% (ITT). This table includes prevalence of each baseline polymorphism, and a summary of number of subjects with polymorphisms in NS3 only, in NS5A only, any in NS3, any in NS5A, any in NS3 or NS5A, any in NS3 + NS5A.
- Total number and percentage of subjects with baseline polymorphisms at a key subset of amino acid positions in NS3 only, in NS5A only, any in NS3, any in NS5A, any in NS3 or NS5A, any in NS3 + NS5A, by subtype, and total (include all subtypes) (ITT).
- Total number and percentage of subjects with baseline polymorphisms at a key subset of amino acid positions in NS3 only, in NS5A only, any in NS3, any in NS5A, any in NS3 or NS5A, any in NS3 + NS5A, by genotype, and total (include all genotypes) (ITT).

**Analysis 2:** The impact of baseline polymorphisms on treatment outcome will be assessed for the mITT-GT-VF population as follows: for each polymorphism, the SVR12 rate will be calculated for subjects with and without the polymorphism and the 2 rates will be compared. Analysis will be grouped by HCV subtype and DAA target (NS3/4A or NS5A).

The following will be included in the analyses of impact of baseline polymorphisms on treatment outcome:

- For each signature amino acid position, presence of any polymorphism at that position (vs no polymorphism at that position), using detection thresholds of both 2% and 15%.
- Each individual polymorphism at each signature amino acid position (vs not that polymorphism) using detection thresholds of 2% and 15%.
- Polymorphism at each non-signature amino acid position (vs. no polymorphism at that position) at a detection threshold of 15%.

**Analysis 3:** In subjects with or without polymorphisms in NS3 only, in NS5A only, any in NS3, any in NS5A, any in NS3 or NS5A, any in NS3 + NS5A at the key subset of

amino acid positions at 15% detection threshold, the SVR12 rate will be calculated for the mITT-GT-VF population, and the rates with or without polymorphisms will be compared using Fisher's exact test. Analysis will be separated by HCV subtype. The following tables will be provided:

- Comparison of SVR12 rates by subtype, and total (include all subtypes)
- Comparison of SVR12 rates by genotype, and total (include all genotypes)

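### mITT-GT-VF keeps early stoppers who reach SVR12 but drops those with measured viraemia, and the SAP plans its stepwise regression and resistance Analyses 2 and 3 on no other population

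*Protocol*

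**What the plan says.** Protocol 8.1 starts from mITT-GT and takes out subjects who did not achieve SVR12 "for reasons other than virologic failure (mITT-GT-VF". SAP 5.1.4 repeats the rule: the population "includes all subjects in the mITT-GT population defined above by excluding subjects who did not achieve" SVR12 for a non-virologic reason. No SVR12 responder is removed, whatever the treatment duration.

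Both documents limit virologic failure to two events. Protocol 8.1.4 has "virologic failure (OTVF or post-treatment relapse"; SAP 10.8 has "on-treatment virologic failure or post-treatment relapse as defined in Section 10.1". SAP 10.1 allows relapse only in subjects who completed treatment, meaning at least 52 days of study drug, or at least 77 days if extended to 12 weeks. A non-responder with shorter dosing and no on-treatment failure falls under reason 4, "Prematurely discontinued study drug with no on-treatment virologic failure", unless classed as a reinfection.

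The uses of the population differ between the documents:
- In the Protocol it serves sensitivity analyses only (8.1, 8.1.2.3). Subgroups are on ITT (8.1.2.4), and resistance Analyses 2 and 3 name no population (8.1.4).
- SAP 10.6 states: "The subgroup analyses will be performed based on the ITT and mITT-GT-VF populations". The stepwise logistic regression in the same section is on mITT-GT-VF alone.
- SAP 10.8, Analysis 2, states: "The impact of baseline polymorphisms on treatment outcome will be assessed for the mITT-GT-VF population". Analysis 3, with Fisher's exact test, uses the same population.

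**The concern.** Take two subjects who both stop on Day 45 with HCV RNA below LLOQ. One stays below LLOQ through the SVR12 window and is kept as a success. The other has confirmed post-treatment viraemia of the same strain and is deleted. Membership of the population then depends on the outcome being analysed.

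This matters most where mITT-GT-VF is the only population. The regression looks for predictors of SVR12, and Analyses 2 and 3 compare SVR12 with and without baseline polymorphisms. Virologic events are expected to be few, so removing one observed event can weaken or distort a comparison. The sensitivity SVR12 rate has the same feature, with less consequence.

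**Working it through.** The plan states no figure on this point. The check is a trace of definitions, followed by illustrations of size.

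**Trace for a subject with fewer than 52 days of study drug (SAP 10.1, 5.1.4, 5.1.2)**

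| Outcome | Class in SAP 10.1 | mITT-GT-VF | PP |
|---|---|---|---|
| Below LLOQ in the SVR12 window, no earlier confirmed rebound | SVR12 responder (timed from last actual dose, no minimum duration) | kept, success | excluded |
| Breakthrough, or end-of-treatment failure with at least 36 days | on-treatment virologic failure | kept, failure | excluded |
| Suppressed at last treatment visit, then same-strain viraemia | reason 4 | dropped | excluded |
| Stopped before Day 36, still at or above LLOQ, no breakthrough | reason 4 | dropped | excluded |
| Missing follow-up | reason 4 | dropped | excluded |

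Without on-treatment failure, the only early stoppers left in mITT-GT-VF are responders, so their rate is 100% by construction. For example, 4 such subjects of whom 2 relapse enter as 2/2 rather than 2/4. PP has no such asymmetry, because it removes early stoppers whatever their outcome.

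**How many subjects?** Protocol 8.2.1 gives 117 + 65 = 182 comparable subjects (treatment-naïve, cirrhotic, 12 weeks), with one non-responder who stopped early. Scaled to this trial, 330 × 1/182 = 1.8. The documents do not say whether that subject was viraemic. All non-virologic failures in the programme were 29/2369 = 1.2%, or about 4 of 330, and only part of these would be measured viraemia after early stopping. I assume 0 to 2.

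**Overall rate.** Assume 5 virologic failures among completers and r viraemic early stoppers, with no other exclusions. As written the rate is (N − r − 5)/(N − r); with the r subjects counted as failures it is (N − r − 5)/N.

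| N | r | As written | Counted as failures |
|---|---|---|---|
| 270 | 1 | 264/269 = 98.14% | 264/270 = 97.78% |
| 270 | 2 | 263/268 = 98.13% | 263/270 = 97.41% |
| 330 | 1 | 324/329 = 98.48% | 324/330 = 98.18% |
| 330 | 2 | 323/328 = 98.48% | 323/330 = 97.88% |

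The shift is 0.3 to 0.7 percentage points. With r = 0 there is none.

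**A small stratum (hypothetical).** Protocol 3.0 gives A30K prevalence in GT3 as 6.3%, and 60 × 0.063 = 3.8, so take 4 carriers and 56 non-carriers. Suppose 2 carriers fail, one of them an early-stop relapse, and 1 non-carrier fails.
- All counted: p = [C(4,2)·56 + C(4,3)]/C(60,3) = 340/34220 = 0.010. Carrier SVR12 is 2/4.
- Early-stop relapse dropped: p = [3·56 + C(3,2)]/C(59,2) = 171/1711 = 0.100. Carrier SVR12 is 2/3.
- If the dropped case were instead the one non-carrier failure: p = C(4,2)/C(59,2) = 6/1711 = 0.0035.

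The distortion can go either way.

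**The case against.** The strongest reply is that the population is meant to isolate virologic efficacy. Relapse after truncated dosing may reflect short exposure rather than baseline sequence, so adding it to a polymorphism comparison brings in noise. For PP, Protocol 8.1.2.1 and SAP 10.3 argue that such exclusions do not help to tell treatment durations apart. This stands as a reason to keep the planned version. It does not justify keeping early stoppers who succeed: excluding short exposure would mean excluding them all, as PP does.

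Three stronger readings are tempting, and the documents support none of them.
- A reader might infer that the trial's main conclusions are biased. They are not: the primary and key secondary analyses use PP and ITT, and ITT counts every such subject as a failure.
- A reader might infer that the subgroup tables are compromised, or that associations with polymorphisms are hidden. The SAP also produces the subgroup tables on ITT. SAP 10.7 lists early stoppers who relapse after suppression, and Analysis 4 in SAP 10.8 covers all SVR12 non-responders with post-baseline resistance data. The cases are visible; they are missing only from the formal comparisons.
- A reader might infer that a large share of virologic events is lost. The programme's rates point to very few cases.

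**Conclusion.** The point holds within limits. Under SAP 5.1.4, as applied in 10.6 and 10.8, inclusion of early stoppers without on-treatment failure depends on whether they reach SVR12. This affects the stepwise regression and resistance Analyses 2 and 3, which have no version on another population, and to a lesser degree the sensitivity SVR12 rate. Early stoppers with breakthrough, or with end-of-treatment failure after at least 36 days, already count as failures and are not part of the problem.

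The likely effect on the overall rate is small. The exposure is in small genotype or polymorphism strata, where a single subject can change the reading. The case counts, the 5 completer failures and the GT3 table are assumptions. This is a worthwhile refinement, not a threat to the trial's conclusions.

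**What to change.** Leave the mITT-GT-VF, PP, ITT and Relapse12 definitions as they are. Redefining mITT-GT-VF would put two meanings of virologic failure in one SAP.

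In SAP 10.6 and 10.8, add a repeat of the stepwise regression and of Analyses 2 and 3. For the repeat, add back to mITT-GT-VF, as failures, every SVR12 non-responder who meets all three conditions:
- study drug duration below 52 days (below 77 if extended);
- measured post-treatment HCV RNA at or above LLOQ, either confirmed or as the last available value;
- not classed as a reinfection.

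Apply this whether or not the subject was suppressed at the Final Treatment Visit, so that those never suppressed are handled the same way. A simpler alternative is to repeat the analyses on mITT-GT, accepting that missing data and reinfections then also count as failures.

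Report both versions. The cost is a few extra tables and a SAP edit, with no protocol amendment. Relapse after short exposure may add some noise, which is why the planned version stays alongside.
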